10.1 Ethical considerations

The CABGpreHAB feasibility study will be conducted in accordance with the protocol after approval from the Committees on Health Research Ethics in the Capital Region of Denmark, and according to good clinical practice guidelines. This study will comply with the General Data Protection Regulation (GDPR) and the Data Protection Act. All personal data collected during this study will be handled confidentially and in accordance with EU legislation and data security regulations and legislation (GDPR). The principles of the Helsinki Declaration in its latest form, and the ICH-GCP guidelines will be followed.¹⁰³ The protocol will be registered on www.clinicaltrials.gov and registered in Privacy before inclusion of the first participant. Substantial

amendments to the protocol will not be implemented without the appropriate review and approval by the regional ethics committee and the Danish Data Protection Agency, with the exceptions of situations where it is necessary to prevent imminent danger to trial participants. In such cases, the amendment will be reported to the regional ethics committee.

10.2 Adverse events and reactions

10.2.1 Definitions

Following definitions will be used.

Adverse Event (AE): any undesirable medical event occurring to a participant during a clinical trial, which does not necessarily have a causal relationship with the intervention.¹⁰⁴

Adverse Reaction (AR): any undesirable and unintended medical response related to the intervention occurring to a participant during a clinical trial.¹⁰⁴

Serious Adverse Event (SAE): any adverse event that results in death, is life-threatening, requires hospitalization or prolongation of existing hospitalization, results in persistent or significant disability or incapacity, or is a congenital anomaly or birth defect.¹⁰⁴

Serious Adverse Reaction (SAR): any adverse reaction that results in death, is life-threatening, requires hospitalization or prolongation of existing hospitalization, results in persistent or significant disability or incapacity, or is a congenital anomaly or birth defect.¹⁰⁴

Suspected Unexpected Serious Adverse Reaction (SUSAR): any suspected adverse reaction which is both serious and unexpected (the nature or severity of which is not consistent with the information available to date).^{104,105}

10.2.2 Risk and safety issues in the current trial

This feasibility study is expected to cause limited risks, side effects and discomfort. Patients are expected to benefit from the homebased multimodal prehabilitation program before CABG-surgery.

10.2.3 Assessment of adverse events

The CABGpreHAB feasibility study will be performed according to the GCP guidelines and applicable regulatory requirements and legislation. The trial will be conducted according to the Act. No.593 of June 14, 2011, on Act on Research Ethics Review of Health Research Projects. The investigator will immediately notify the regional ethics committee if there, within the intervention period, occur SAEs, SARs or SUSARs. The report will be accompanied by comments on possible implications for the trial, and notification will be made within 7 days after investigator has knowledge of the event. In case of serious adverse reactions, which are results of the trial, the investigator will provide the regional ethics committee with the information required.

Throughout the trial, annual reports including all expected or unexpected adverse events or reactions will be submitted to the ethical committee. Reports will be accompanied by an assessment of the participants safety.

10.2.4 Severity of adverse events

The following variables will be registered if an adverse event happens: Description of the event, beginning and ending of the event, seriousness (mild, moderate, and serious). Possible causal relation to the intervention and actions taken. This will be registered by a project employee and a physician will be involved if a serious event occurs or if required in relation to a moderate adverse event.

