Safety: Safety of the intervention will be determined based on the number and nature of adverse events (AE), which is defined as any discomfort or symptoms of angina pectoris that will prevent a patient to take part in the physical tele exercise sessions or symptoms that require medical attention. Adverse event (AE), serious AE (SAE), serious adverse reaction (SAR), and suspected unexpected serious adverse reaction (SUSAR) will be monitored during the trial counting the number of occurrences. In addition to the physiotherapist

taking note of any undesirable effect during and after the tele session or phone counselling with the project nurse, all participants are asked to report any symptoms that was not consistent with their usual physical condition presentation as a result of exercise sessions.

For a lager RCT trial to be deemed feasible, feasibility outcomes need to be attained, meaning that more than 60% of eligible patients will participate and at least 52% of the intervention group will receive more than 60% of the intended interventions.⁸⁷

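### Section 10.2.4 grades adverse events on one item that puts the outcome-based category 'serious' at the top of an intensity scale, so some events are graded wrongly whichever way the word is read

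*Protocol*

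**What the plan says.** Four parts of the protocol bear on this point.

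- **Section 10.2.4.** The heading is "10.2.4 Severity of adverse events", but the graded variable beneath it is "seriousness (mild, moderate, and serious". The other listed items are a description, start and end, possible causal relation and actions taken. On who does the recording: "This will be registered by a project employee". On escalation: "a physician will be involved if a serious event occurs or if required in relation to a moderate adverse event".
- **Section 10.2.1.** An SAE is "any adverse event that results in death, is life-threatening, requires hospitalization or prolongation of existing hospitalization", or one that leads to lasting or significant disability or to a congenital anomaly. Intensity plays no part in the definition.
- **Section 7.1.** Safety is listed among the primary feasibility outcomes. AEs, SAEs, SARs and SUSARs "will be monitored during the trial counting the number of occurrences".
- **Section 10.2.3.** The investigator must at once "notify the regional ethics committee if there, within the intervention period, occur SAEs, SARs or SUSARs", with a limit of 7 days from learning of the event.

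**The concern.** Intensity and seriousness are different attributes of an event. A mild event can lead to an admission, and a severe one can pass without meeting any SAE criterion. Section 10.2.4 merges them: its heading speaks of severity, its variable is named seriousness, its two lower levels are intensity grades, and its top level is a word that 10.2.1 has already defined by outcome. The section does not say which meaning applies, so two members of staff could code the same event differently.

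Two things are at stake. The first is the safety description in a pilot whose purpose is to prepare a larger RCT: intensity, or seriousness, or both cannot be read reliably from this item. The second is that physician involvement is worded in the terms of this scale. It is stated for a serious event, conditional for a moderate one, and not mentioned for a mild one.

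**Working it through.** No arithmetic applies. The check is to cross the two attributes, which gives six kinds of event (three intensities, SAE criterion met or not), and to see where each lands under the two possible meanings of *serious*. The intensity levels mild, moderate and severe are the usual ones; the protocol itself names only the first two.

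**Reading A:** *serious* means the SAE category of 10.2.1.
**Reading B:** *serious* means severe intensity, as the heading of 10.2.4 suggests.

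| Intensity | 10.2.1 criterion met? | Recorded under A | Recorded under B |
|---|---|---|---|
| Mild | No | Mild, correct | Mild, correct |
| Moderate | No | Moderate, correct | Moderate, correct |
| Severe | No | No level fits | Serious, although not an SAE |
| Mild | Yes | Serious; intensity lost | Mild, although an SAE |
| Moderate | Yes | Serious; intensity lost | Moderate, although an SAE |
| Severe | Yes | Serious; intensity lost | Serious, correct |

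**Under A**, four of the six kinds are incompletely or wrongly recorded: one has no level, and the three kinds of SAE lose their intensity. No SAE is missed, and the physician sentence covers every SAE.

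**Under B**, intensity is kept, but three of the six kinds carry a label that disagrees with 10.2.1. Two of these are SAEs filed below *serious*. For the moderate one, physician involvement becomes conditional; for the mild one, 10.2.4 says nothing. A short admission for chest pain of moderate intensity is an example: it meets the criterion "requires hospitalization or prolongation of existing hospitalization" yet would be filed as moderate.

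**Does either reading reach the SAE count or the notification?** Not formally. Sections 7.1 and 10.2.3 both use the term SAE, which 10.2.1 defines, and neither refers to the three-level item. The link is practical: someone must judge whether the 10.2.1 criteria are met, and the variables listed in 10.2.4 include no item in which that judgement is recorded, unless the mixed item is taken to be it.

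**The case against.** The strongest reply is that the protocol defines an SAE correctly and states at the start of 10.2.1 that its definitions are the ones to be used. That favours reading A, under which a mild event with admission is serious by definition, is counted, and brings in a physician. Only an intensity grade is lost. This has weight, and it means the two harms must be put as alternatives: missing grades belong to reading A, SAEs filed too low to reading B. It does not settle the matter, because the heading and the two lower levels of 10.2.4 point to intensity and the section never says otherwise.

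There are also safeguards. Section 8.2 has adverse events in the intervention period taken from the patient record and has records reviewed for safety endpoints, so an admission would probably come to light. Section 9.1 reports adverse events with text as well as numbers and percentages. Section 10.2.3 requires annual reports with a safety assessment. The eCRF is still to be built (11.1) and may carry a separate SAE field. These points stand as partial protection. None of them corrects the recording rule as written or supplies the missing intensity grade.

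A reader might infer something stronger: that SAE counts and ethics committee notification are driven by this item, so that SAEs will go uncounted or unreported. The documents do not support that. Both rest on the definitions in 10.2.1, and staff who apply those definitions directly would count and notify correctly whatever was entered on the three-level item. Nor would one misfiled event change a stated decision: the summary criteria for a larger RCT in 7.1 concern participation (more than 60% of eligible patients) and receipt of the intervention (at least 52% of the group receiving more than 60% of it), with no safety threshold.

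**Conclusion.** The point holds as an inconsistency between 10.2.4 and 10.2.1. A single item cannot carry both attributes, and under each reading some kinds of event are misgraded: four of six under A, three of six under B. Those are counts of event types, not forecasts of how many events will be affected. The protocol gives no expected frequency or mix of adverse events, so the practical size cannot be estimated.

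The consequence is limited to the description of safety, one of the primary feasibility outcomes, and to the physician-involvement sentence. Sample size, error rates and the stated criteria for a larger RCT are unaffected. The conclusion assumes that the items listed in 10.2.4 are those that will be recorded; if the eCRF already separates the two attributes, only the wording is at fault. It is worth correcting before recruitment because the change is very small.

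**What to change.** - Replace the single item in 10.2.4 with two: intensity (mild, moderate, severe), and serious yes/no judged by the 10.2.1 criteria.
- State that SAE counts under 7.1 are taken from the second item, and report both items.
- Reconcile the physician-involvement sentence in 10.2.4 with 10.2.1 and 10.2.3, so that it is clear which of the two attributes it refers to. Which events call for a physician is for the sponsor to decide and is not proposed here.

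The cost is one extra eCRF field and a reworded sentence, with no effect on visits, sample size or analysis.

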10.3 Risks and benefits

The interventions are expected to cause limited risks, side effects and discomfort. Patients are expected to benefit from homebased prehabilitation due to multimodal preoperative preparation before CABG-surgery improving functional capacity, reducing symptoms of anxiety and depression. Individualized and optimized preoperative care through exercise, supportive nursing counselling will be performed by experienced project nurses, physiotherapists and physicians, and patients will not experience any kind of delays or complications related to the interventions or follow-up process due to participation in the project. Before commencing the exercise components of the prehabilitation program, a physiotherapist will assess the participants' physical capacity. Previous studies have demonstrated the safety of preoperative physical exercise programs involving mild intensity training in patients scheduled for CABG surgery.^{6,27,106,107} The physical training regimen will adhere to the established recommendations for physical exercise in patients awaiting CABG surgery, ensuring the safety and efficacy of the exercise program.^{108,109} Standard blood sampling, which may cause slight discomfort from the needle stick, is expected as part of the procedure.

10.3.1 Risk and timing of surgery

Historically waiting time for elective CABG surgery has usually been several weeks, but it has been fluctuating between few weeks and up to months. The decision regarding the timing of surgery is typically made collaboratively by cardiologists and cardiac surgeons during multidisciplinary team (MDT) conferences.¹⁹ This decision-making process adheres to current clinical guidelines and is influenced by waiting times dictated by local and regional healthcare resources. According to the most recent guidelines published by the American College of Cardiology, the prioritization and assessment of patient risk before surgery are central to MDT discussions.²⁰ For patients with stable angina, timely surgical intervention is advised to prevent progression to acute coronary events.^{110,111} In a Danish context, there is a 30-day recommendation for maximum waiting times for elective CABG surgery.¹¹³

10.4 Ensuring integrity and privacy of the participant

All patient-related information obtained during the feasibility study will be handled in accordance with the Danish law for protection of personal data ("lov om behandling af personoplysninger")¹¹³ and the Danish health law (" sundhedsloven"). The

10.5 Oral information and informed consent

Prior to consent all participants receive written and oral information about usual care and the interventions included the CABGpreHAB feasibility study, including the Ethics Committee folder "Forsøgspersonens rettigheder i et sundhedsvidenskabeligt forskningsprojekt".¹¹⁴ The participant is informed about the right to bring an assessor and the right to consider their participation for a minimum of 24 hours if needed. The oral information of the patient and signing of the informed consent form will be conducted in a closed off room to ensure that the information is given under undisturbed circumstances and are carried out by the investigator or substitute directly involved in the trial, who have the necessary experience and competence. When the information is given, it is emphasized that participation is voluntary. A patient can be withdrawn from the study at any time, if it is the wish of the patient, or if it is medically indicated, as judged by the investigator. Participation in the study is discontinued, if any of the following criteria applies a) the patient's general condition contraindicates continuing the study or b) the patient turns out to be non-eligible patient.

11. Legal and organizational aspects

11.1 Quality control and quality assurance

All data will be entered into a study database for analysis and reporting. Any data captured electronically will be stored electronically in a separate database according to standard procedures at Rigshospitalet. Upon completion of data entry, the databases will be checked to ensure acceptable accuracy and completeness. System backups and record retention for the study data will be consistent with Rigshospitalet's standard procedures. Source data will be recorded in the electronic patient record or on specific worksheets. An electronic Case Report Form (eCRF) will be constructed for data capture. The investigators are responsible for ensuring the accuracy, completeness, legibility, and timeliness of the data recorded in the eCRFs.

11.2 Economy

The study is an investigator-initiated trial conceived and conducted by The Department of Cardiothoracic Surgery, The Heart Centre, Copenhagen University Hospital. The idea for the project originated from [name] and the department of Cardiothoracic surgery at the Heart Centre at Rigshospitalet. The trial will be funded by external funds for research in health sciences. All grants will be paid to the financial office at Rigshospitalet and will be used for salaries for the trial staff and other research related to expenses. No compensation is granted to trial participants or transport expenses. None of the persons responsible for the trial have any

financial affiliation with the funds applied for. If such funding is achieved the ethical committees will be informed of the donator, and value of the grant, and the written patient information material will be updated with all donators mentioned. Any received funds will be deposited to a project specific research account, which is administrated by the hospital and under public revision. The CABGpreHAB trial has been supported by research grants from: The Heart Centre research foundation on the amount of 204.000 DKK, Helsefonden 300.000 DKK (ID: 23-B-0122), Trygfonden 600.000 DKK (ID159457) and PhD. Stipendium from Rigshospitalet Forskningspulje. These funds are used for salaries, running costs and equipment during the project period.

11.3 Insurance

According to the Act on right of appeal and compensation within the National Health Service (Act No. 547 of 24 June 2005) all trial participants are covered by the Patient Assurance Association and will be informed about this prior to inclusion. Sponsors, researchers, and trial nurse are covered by the statutory insurance at the hospital.

11.4 Plan for publication, authorship, and dissemination

After approval of the ethics application by the Regional Scientific Committee, The Capital of Copenhagen, the feasibility study will be registered on www.ClinicalTrials.gov before randomization of patients start. Results of the study will be analyzed by an independent statistician, and the results will be interpreted by the research group. The conclusion will be prepared in in two versions, before the allocation code is broken, with the two arms alternately assumed as intervention (one that assumes that arm A is the intervention, and second, that assumes that the arm B is the intervention). Positive, negative and inconclusive results of the CABGpreHAB feasibility study will be published. The final manuscripts emanating from the study will be sent to a “peer reviewed” international journal. Authorship will be allocated using the guidelines for Proposal authorship defined by the international Committee of medical journal Editors and depends on the personal involvement. A minimum of three scientific papers are planed based on CABGpreHAB trial. To reach policy makers, administrators and healthcare professionals, the project will be presented in thoracic surgery, cardiology, nursing, and physiotherapy journals. To gain broader interest, national patient associations will be contacted.

